1. LIST OF ABBREVIATIONS AND RELEVANT DEFINITIONS

ACS	Acute coronary syndrome
ASCVD	Atherosclerotic cardiovascular disease
CFS	Clinical Frailty Score
CVE	Cardiovascular event
CVRM	Cardiovascular Risk Management
ESC	European Society of Cardiology
LDL-C	Low density lipoprotein cholesterol
LLT	Lipid Lowering Therapy
NSTEMI	Non-ST-Elevation Myocardial Infarction
PCSK9-i	Proprotein convertase subtilisin/kexin type 9 inhibitors
Sponsor	The sponsor is the party that commissions the organisation or performance of the research, for example a pharmaceutical company, academic hospital, scientific organisation or investigator. A party that provides funding for a study but does not commission it is not regarded as the sponsor, but referred to as a subsidising party.
STEMI	ST-Elevation Myocardial Infarction
T2DM	Type 2 Diabetes Mellitus
WCN	Werkgroep Cardiologische centra Nederland
WMO	Medical Research Involving Human Subjects Act (in Dutch, Wet Medisch-wetenschappelijk Onderzoek met mensen)

2. ABSTRACT

Rationale: Guideline recommended evidence-based clinical care correlates with improved patient outcomes. In real life care, however, adherence to guideline recommendations remains suboptimal. In real life, patients may receive suboptimal treatment and as a result treatment targets are not always met. To support and improve secondary prevention for cardiovascular disease, PENELOPE and PENELOPE-CTRL are designed to support guideline implementation on lipid management and provide valuable feedback to care-givers on real world data.

The recent PENELOPE study was designed to determine the effect of a protocolized, Dutch-, and European Society of Cardiology (ESC) guidelines based strategy of stepwise intensified lipid management in patients at very high risk for Acute coronary syndrome (ACS). In PENELOPE 22 Dutch non-academic hospitals, members of the WCN investigator network, implemented a protocol guided guideline approach in a consecutive cohort of very high-risk patients admitted for ACS over the period 01-01-2019 to 31-08-2020. Lipid values and medication strategy are collected at baseline (index ACS), and after three months and one year post ACS, in order to establish the percentage of patients on target Low density lipoprotein cholesterol (LDL-C).

The current PENELOPE-CTRL study on the other hand, is designed to serve as a contemporary control cohort for PENELOPE. PENELOPE-CTRL is a retrospective observational study, creating a contemporary snapshot of real-life lipid management for secondary prevention in very high-risk patients. PENELOPE-CTRL will collect data in similar hospitals who did not participate in the PENELOPE trial.

To allow comparison of these two strategies, protocol guided versus real life implementation of the cholesterol treatment guidelines, both cohorts include similar patients, and similar data will be collected (e.g., lipid lowering drugs, lipid panels) . Analysis will be done at similar time points. Comparing the real-life data from PENELOPE-CTRL with the data from the PENELOPE study will quantify the effect of a strategy of protocolized guideline-based lipid management with regards to the incidence of target LDL-C levels in very high-risk patients, 3 months and one year after hospitalisation with a myocardial infarction.

Objective: To measure real life lipid lowering therapy (LLT) and resulting LDL-C levels in very high-risk patients. PENELOPE-CTRL will be used as a control cohort versus protocolized (PENELOPE study) implementation of the Dutch and ESC guidelines.

Study design: Retrospective cohort study.

Study population: Patients with a history of **Atherosclerotic cardiovascular disease (ASCVD)** and/or type 2 diabetes (T2DM), admitted for a type I ST-elevation myocardial infarct (STEMI) or non-STEMI. Patients <18 years or >70 years of age will be excluded.

In PENELOPE patients over 70 were included based on a frailty index. As this parameter cannot be determined retrospectively, patients over 70 will be excluded from the CTRL cohort, as well as from the comparative analysis for the two cohorts.

Study parameters: Cardiovascular medical history and risk profile, baseline characteristics (including index event, lipid panels, baseline medication and LLT); and follow up data on LLT and lipid panels during the year post ACS

Nature and extent of the burden and risks associated with participation, benefit and group relatedness: None, retrospective data collection.

3. INTRODUCTION AND RATIONALE

One of the main underlying causes of atherosclerotic cardiovascular disease is the retention of LDL-C and other cholesterol containing lipoproteins within the arterial wall. There is an approximately linear relationship between the absolute reduction in LDL-C and the proportional reductions in the incidence of coronary and major vascular events.[1] Clinical trials have clearly shown that the lower the achieved LDL-C values, the lower the risk of future cardiovascular events. Guidelines summarize and evaluate available evidence with the aim of assisting health professionals in proposing the best management strategies for an individual patient with a given condition.[2, 3] For secondary prevention in very-high-risk patients the 2016 ESC Guidelines for the management of dyslipidaemia recommended an LDL-C reduction to <1.8 mmol/l.[1] in the 2019 ESC Guidelines this was narrowed down even further to <50% from baseline and an LDL-C goal of <1.4 mmol/L.[4] If the LDL-C goal is not achieved 4 - 6 weeks after the cardiovascular event (CVE) despite maximal tolerated statin therapy, ezetimibe should be added first, followed by Proprotein convertase subtilisin/kexin type 9 inhibitors (PCSK9-i). [3] The Dutch Cardiovascular Risk Management (CVRM) guideline (in the period PENELOPE was performed) recommends an LDL-C goal of at least <1.8 mmol/L for very high-risk CV-patients.

Adherence to treatment guidelines is a predictor of fewer CV hospitalizations. In real life care, however, compliance to guidelines for secondary prevention of cardiovascular disease, can be improved according to recent European and Swedish national studies. [5-8] A strategy of protocolized, Dutch- and ESC-guideline based stepwise approach in lipid lowering therapy (LLT) to reach target LDL-C in very high-risk patients was studied in the PENELOPE study. Protocolized LLT consisted of 3 steps, with LDL-C levels measured \geq 4 weeks after each step:

- Step 1: if at baseline LDL-C >1.8 mmol/L, then a high intensity statin (HIST), defined as atorvastatin \geq 40 mg OD or rosuvastatin \geq 20 mg OD, had to be initiated.
- Step 2: if \geq 4 weeks after step (1) LDL-C >1.8 mmol/L, then ezetimibe 10 mg OD had to be initiated.
- Step 3: if \geq 4 weeks after step (2) LDL-C >1.8 mmol/L alirocumab had to be initiated following pre-specified criteria:
 - if LDL-C 1.8-2.6 mmol/L, addition and dosing of alirocumab was left at the investigator's discretion
 - if LDL-C 2.6-3.6 mmol/L, alirocumab 75 mg or 150 mg Q2W had to be initiated (dosing at the investigator's discretion)
 - if LDL-C >3.6 mmol/L, alirocumab 150 mg Q2W had to be initiated.

PENELOPE was designed to demonstrate feasibility and efficacy of guideline-based protocolized LLT in the Netherlands.

PENELOPE-CTRL is designed to document real life LLT and resulting LDL-C target attainment in the Netherlands.

Comparison of PENELOPE and PENELOPE-CTRL will demonstrate whether the strategy of protocolized guideline based LLT results in a higher incidence of target LDL-C levels in secondary prevention at set time points, and quantify this difference.

4. OBJECTIVES

Primary Objective:

To compare real life LLT and reaching target LDL-C levels in very high-risk patients versus protocolized (PENELOPE study) implementation of the current Dutch and ESC guidelines.

5. STUDY DESIGN

PENELOPE-CTRL is designed as a retrospective cohort study with its enrolment-period coinciding with the inclusion period of PENELOPE, i.e. January 1st, 2019 until August 31st, 2020.

6. STUDY POPULATION

a. POPULATION

All patients fulfilling the in- and exclusion criteria in the participating centres will be included in the PENELOPE-CTRL cohort (Registry). Participating sites are part of the WCN research network and have not participated in PENELOPE. These are all non-academic cardiovascular research centres, providing regional cardiovascular hospital care with a regional CVRM function. All sites are using the same standard operating procedures for clinical research.

Inclusion criteria are identical to the Penelope trial, with the exception of the introduction of a maximum age of 70 years in PENELOPE-CTRL. (Table 1) In PENELOPE, patients >70 years of age were required to have a clinical frailty score (CFS) ≤ 3 . As retrospective electronic medical records data do not allow for accurate determination of the CFS, all patients >70 years will be excluded in PENELOPE-CTRL. For the comparative analysis the CTRL population will be compared to the Penelope patients ≤ 70 years old (N=663). Furthermore, only patients who were alive at discharge will be registered.

b. INCLUSION CRITERIA

- Age >18 and ≤ 70 years
- Alive at hospital discharge after admission for (N)STEMI between 1-1-2019 and 31-08-2020

- Planned for follow-up at a participating PENELOPE CTRL site
- History of T2DM and/or history of ASCVD defined as either one of:
 - cerebrovascular disease/ event: transient ischemic attack, cerebral infarction, amaurosis fugax, retinal infarction
 - Coronary artery disease/ event: unstable angina pectoris, MI, ACS, coronary revascularization (coronary angioplasty or surgical procedure for coronary bypass)
 - Peripheral artery disease (symptomatic and documented obstruction of a distal extremity artery or surgical intervention (percutaneous transluminal angioplasty, bypass or amputation)

Table 1. Inclusion criteria PENELOPE and PENELOPE CTRL, and PENELOPE analysis population

	PENELOPE	PENELOPE (cohort compared to CTRL)	PENELOPE CTRL
Age	≥18 years, ≤70 years	≥18 years, ≤70 years	≥18 years, ≤70 years
	>70 years and CFR≤3	-	-
history of ASCVD	✓	✓	✓
T2DM	✓	✓	✓
admission for (N)STEMI	✓	✓	✓

c. EXCLUSION CRITERIA

- Pregnant and lactating women

Participation in lipid modifying drug trials up to two years after index CVE.

d. PATIENT SELECTION

All eligible patients will be identified for data capture in the participating PENELOPE CTRL centers by the local team of the PI. Eligible patients will be pre-identified from local electronic health records using text-mining (CT-cue) on the in- and exclusion criteria. A local member of the study team will confirm eligibility based on the detailed structured and non-structured local electronic health record data. A feasibility query in participating centres shows a cohort of 700-1200 candidates.

7. DATA COLLECTION

The following data will be collected from the local electronic health record starting at admission up to 18 months:

- Baseline characteristics including at least age at admission, index event, medical history and cardiovascular risk factors
- Lipid lowering medication, including start and stop dates, (perceived) cause of interruption or intolerance, and dosage
- Lipid panels: all available total cholesterol, LDL, HDL, and TG values will be collected
- Clinical course, including death, myocardial infarction, stroke and (urgent) revascularisation and co-medication

8. STUDY OUTCOMES

a. PRIMARY STUDY OUTCOME

The primary outcome is defined as the cumulative incidence of patients reaching the LDL-C target level (≤ 1.8 mmol/L) after admission for a type I (N)STEMI with oral lipid lowering medication only, compared to the designated PENELOPE cohort.

Further details on handling of missing or out of window values collected from regular care will be detailed in the endpoint charter, used for endpoint adjudication.

After analysis of the PENELOPE CTRL data the CTRL cohort will be compared to the original PENELOPE cohort.

b. SECONDARY STUDY OUTCOMES

- a) Mean time of reaching the primary outcome, compared to the designated PENELOPE cohort.
- b) Cumulative incidence of patients reaching the LDL-C target level (≤ 1.8 mmol/L) within 90 days after admission for a type I (N)STEMI with oral lipid lowering medication only. This outcome will be estimated with two analysis:
 - only including patients reaching (at least once) LDL-C target within 90 days (without using LDL-C measurements after this window) and
 - additionally including the first available LDL-C measurement (at least 14 days) after the last modification in oral lipid lowering therapy within 90 days after baseline (even if this measurement is after 90 days). This way CTRL mimics the original PENELOPE dataset, where LDL measurement 4-6 weeks after a drug regimen change was mandatory to establish the treatment effect, and this measurement also includes the effect of the last drug regimen change within 90 days.

- c) Cumulative incidence of patients reaching other LDL-C target levels (e.g. ≤ 1.4 mmol/L and 50% LDL-C reduction compared to baseline) and mean LDL-C levels with only oral medication after admission for a type I (N)STEMI, compared to the designated PENELOPE cohort.
- d) Cumulative incidence of reaching LDL-C target levels (≤ 1.8 mmol/L, ≤ 1.4 mmol/L and 50% LDL-C reduction) compared to baseline) and mean LDL-C levels with any lipid lowering drugs (so including the effects of PCSK9i), compared to the designated PENELOPE cohort.
- e) Cumulative incidence of patients reaching LDL-C target levels with only (i) high-intensive statin (compared to cum. effect after STEP 1 in PENELOPE) or (ii) high-intensive statin and/or ezetimibe (compared to cum. effect after STEP 2 in PENELOPE).

c. STUDY PROCEDURES

As PENELOPE-Control is a retrospective cohort registration there are no study procedures.

d. Randomisation, blinding and treatment allocation

Not applicable.

e. Withdrawal of individual subjects

Not applicable.

f. Premature termination of the study

Not applicable.

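### The primary cumulative incidence (8a) has no end date, 8b(a), (c), (d) and (e) share the gap, and a mean time to target is undefined for patients who never reach it

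*Protocol*

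**What the plan says.** Section 8a: "The primary outcome is defined as the cumulative incidence of patients reaching the LDL-C target level" of 1.8 mmol/L or lower on oral therapy, counted from admission. It gives a start and no end. It leaves the handling of missing and out-of-window values to an endpoint charter but states no window.

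In Section 8b, only outcome (b) closes a window, at 90 days. Outcome (a) is the mean time of reaching the primary outcome. Outcomes (c), (d) and (e) are further cumulative incidences without an end date.

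The intended timing appears elsewhere:

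- Section 2, Rationale: the comparison concerns the "incidence of target LDL-C levels in very high-risk patients, 3 months and one year after hospitalisation", and "Analysis will be done at similar time points".
- Section 2, Study parameters: "follow up data on LLT and lipid panels during the year post ACS".
- Section 3: the question is whether the strategy "results in a higher incidence of target LDL-C levels in secondary prevention at set time points". The time points are not named.

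The data actually collected for CTRL run longer. Section 7 states: "The following data will be collected from the local electronic health record starting at admission up to 18 months", and for lipid panels "all available total cholesterol, LDL, HDL, and TG values will be collected". PENELOPE lipid data are described at baseline, three months and one year (Section 2), with step-triggered readings in between (Section 3: "Protocolized LLT consisted of 3 steps, with LDL-C levels measured" at least four weeks after each step).

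Section 10 removes patients who start a PCSK9 inhibitor from the primary outcome and from outcomes b, c and e. It does not list outcome a.

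**The concern.** A cumulative incidence can only stay level or rise as follow-up lengthens. If CTRL patients may be credited with a first value at target in months 13 to 18 while PENELOPE data stop at one year, the two proportions do not describe the same period. On follow-up length alone, that raises the CTRL proportion and understates the effect of the protocolised strategy. The primary contrast then depends on a cut-off that its own definition does not fix. Because both cohorts lie in the past, that cut-off could also be chosen after data have been seen.

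The mean time in 8b(a) has a second defect, which remains even with equal follow-up. A patient who never reaches target has no time to average. If the mean is taken over reachers only, a cohort that brings additional patients to target at a later step can appear slower than one that leaves those patients above target.

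**Working it through.** **No figure to reproduce.** The Protocol gives no attainment rate, expected difference or power calculation. What follows is an illustration. From the Protocol: 663 PENELOPE patients aged 70 or younger (Section 6a), 700 to 1,200 CTRL candidates (Section 6d), extraction to 18 months (Section 7), PENELOPE described to one year (Section 2). Assumed: CTRL attainment p at 12 months of 40% to 80%, and a hazard of reaching target after month 12 equal to a fraction f (0.1 to 1) of the first-year average. Removal at PCSK9 inhibitor start is not modelled.

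**Step 1: gain from m extra months.** With h = −ln(1 − p)/12, the added points are 100 × (1 − p) × (1 − exp(−m × f × h)). At p = 0.60, h = 0.916/12 = 0.0764 per month. For m = 6 and f = 1: 100 × 0.40 × (1 − exp(−0.458)) = 14.7 points.

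| Extra months (p = 60%) | f = 0.10 | f = 0.25 | f = 0.50 | f = 1 |
|---|---|---|---|---|
| 3 | 0.9 | 2.2 | 4.3 | 8.2 |
| 6 | 1.8 | 4.3 | 8.2 | 14.7 |

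Over p = 40% to 80% and f = 0.1 to 1, the gain is 0.3 to 2.9 points for 1 month, 0.8 to 8.2 for 3 months and 1.5 to 14.8 for 6 months. The shorter gaps are shown because the Protocol gives no window for PENELOPE's one-year reading.

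**Step 2: scale.** The 95% half-width of a difference between two proportions near 60% is 196 × √(0.24 × (1/663 + 1/n)). This is 5.2 points for n = 700 and 4.6 for n = 1,200.

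**Step 3: when the shift exceeds that.** Set the gain equal to the half-width w (as a proportion) and solve: f = ln(0.40/(0.40 − w))/(m × h).

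- 6 months: f = 0.30 (n = 700) or 0.27 (n = 1,200).
- 3 months: f = 0.61 or 0.54.

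So at 60% attainment, a later hazard of a quarter of the first-year average or less keeps the shift inside the half-width.

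**Step 4: mean time with equal follow-up (invented example).** Cohort A has 60% at target at week 6 and a further 25% at week 12. Cohort B has 60% at week 6 and no more.

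- Mean over reachers: A = (0.60 × 6 + 0.25 × 12)/0.85 = 7.8 weeks; B = 6.0 weeks. A looks slower although it does at least as well at every time.
- Restricted mean to week 52, non-reachers counted at 52: A = 0.60 × 6 + 0.25 × 12 + 0.15 × 52 = 14.4 weeks; B = 0.60 × 6 + 0.40 × 52 = 24.4 weeks. The order is now right.

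**The case against.** The best defence is that one year is plainly meant. The Abstract names three months and one year, outcome 8b(b) takes the three-month point, and one year is what remains for 8a. Section 7 sets an extraction window, not an analysis window, and 8b(b) itself gives a reason to extract past a cut-off, since it may use a reading taken after day 90. Section 10 leaves statistical methods to the SAP, which was not available for this review, and the charter is to deal with out-of-window values.

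Much of this stands. A reader might infer that the study plans to set 18 months of CTRL against 12 months of PENELOPE. The documents do not support that: the Abstract states the opposite intention, and no sentence says that values after one year will count. What does not stand is that the deferrals close the gap. The charter is announced for handling values outside a window, not for setting the window, and the SAP for methods. The horizon is part of the definition of a primary cumulative incidence and belongs in the Protocol.

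It is also fair to say that a mean among reachers can be read as a descriptive figure beside the cumulative incidence, and that the estimator for a secondary outcome may be left to the SAP. That makes this the lesser part. Still, 8b(a) already fixes the measure as a mean, to be compared between cohorts.

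**Conclusion.** The point holds as an open definition that permits unequal follow-up; it does not show that unequal follow-up is planned. It should be fixed: the primary outcome and 8b(a), (c), (d) and (e) lack an end date, and the CTRL data as collected run six months past the period described for PENELOPE.

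A reader might take about 15 points as the likely bias. The documents do not support that. It needs a full six-month gap and a hazard that does not fall after month 12, and both attainment and hazard are assumed. With the later hazard at a quarter or less and 60% attainment, six months add at most 4.3 points, inside the 4.6 to 5.2 point half-width. Nor can the net direction be taken as settled. Follow-up length alone favours CTRL, but PENELOPE required readings after regimen changes while CTRL relies on routine care, and removal at PCSK9 inhibitor start also ends time at risk.

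The mean-time defect does not depend on the horizon: the measure has no value for non-reachers, and the example shows that a reachers-only mean can reverse the order. How often that would happen here is unknown.

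**What to change.** - **Section 8a:** define the outcome as *cumulative incidence by one year after admission, with the same measurement window in both cohorts*. Apply the same horizon to 8b(a), (c), (d) and (e).
- **Section 7:** say that CTRL values after that window are not used in the comparison, and reconcile the 18 months with the one year under Study parameters in the Abstract.
- **Section 8b(a):** replace the mean with the cumulative incidence curve, or with a restricted mean time to target up to the same horizon. A median serves only if at least half of each cohort reaches target.
- **Section 10:** add outcome a to the list, and state how PCSK9 inhibitor start and death before target are handled, identically in both cohorts. One option is to treat them as competing events, counted as not reached on oral therapy. Without such a rule, a restricted mean over all patients would be undefined for those removed at PCSK9 inhibitor start.

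The cost is wording, carried into the endpoint charter and SAP; no further extraction from CTRL records is needed. The downside is that some late CTRL values go unused in the comparison. The window must also fit the measurement dates PENELOPE actually holds, which the Protocol does not show and which should be checked before the window is fixed.

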10. STATISTICAL ANALYSIS

The primary analysis consists of a comparison of outcomes between de PENELOPE CTRL and the original PENELOPE intention to treat population. Baseline characteristics of the cohorts will be presented. To assess for potential remaining imbalances between the cohorts a t-test and Chi-squared test will be used for continuous and dichotomous variables, respectively.

In case of imbalance in patient characteristics between the cohorts, a step-wise approach will be used to correct for this.

- First, a propensity score is derived to asses for membership of trial. Second, a propensity score is derived on the baseline criteria.
- If the distribution of the propensity scores is dissimilar between PENELOPE CTRL and PENELOPE adjustment for differences in propensity function is done in two methods.
 - First, logistic regression analysis with propensity score as co-variate.
 - Second, stratified analysis with deciles of the propensity score.

Percentages are converted to Odds Ratio to allow for multivariable analysis. Missing values are reported and appropriately imputed in the statistical models.

Statistical analysis will be formalised in the SAP, as well as the statistical methods to be used for endpoint analysis. For comparison between the PENELOPE and PENELOPE CTRL cohort, the same additional exclusion criteria were applied: 'known intolerance for alirocumab' and 'active PCSK9-I therapy at baseline'. Life expectancy <1 year was omitted as this could not be determined reliably from the medical records retrospectively. For the primary outcome and secondary outcomes b, c and e (investigating the effects of oral LLT), patients will be excluded as soon as they start using PCSK9i.

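### Adjustment for baseline LDL-C in the primary comparison depends on a balance test, so a moderate difference in the share already at or below 1.8 mmol/L can go uncorrected

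*Protocol*

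**What the plan says.** - **Outcome (Protocol 8a).** The primary outcome is the "cumulative incidence of patients reaching the LDL-C target level (≤ 1.8 mmol/L) after admission for a type I (N)STEMI", on oral lipid-lowering medication only. The baseline value plays no part in the definition.
- **Eligibility (Protocol 6b).** Entry rests on age, survival to discharge after (N)STEMI, planned follow-up at the site and "History of T2DM and/or history of ASCVD defined as either one of" several vascular conditions. There is no LDL-C threshold.
- **Extra exclusions for the comparison (Protocol 10).** These are given as "the same additional exclusion criteria were applied: 'known intolerance for alirocumab' and 'active PCSK9-I therapy at baseline". Neither concerns baseline LDL-C.
- **PENELOPE strategy (Protocol 3).** The first step reads "if at baseline LDL-C >1.8 mmol/L, then a high intensity statin (HIST" and so on. Steps 2 and 3 likewise start only from LDL-C above 1.8 mmol/L.
- **Adjustment (Protocol 10).** After t-tests and chi-squared tests on baseline characteristics, "In case of imbalance in patient characteristics between the cohorts, a step-wise approach will be used to correct for this". The correction is a propensity score built on unspecified baseline criteria, used as a covariate in logistic regression and then in deciles. It is applied if the score distributions are dissimilar; no criterion for dissimilarity is given.
- **Data (Protocol 2 and 7).** Lipid panels and baseline lipid-lowering therapy are listed among the baseline characteristics in the abstract, and all available lipid values are collected.

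**The concern.** All patients have prior ASCVD or T2DM, so some can be expected to arrive on lipid-lowering therapy and already at or below 1.8 mmol/L. The conditional first step of PENELOPE foresees such patients. They are likely to show a value at or below 1.8 after admission whichever cohort they are in, and the strategy asked for nothing at entry. Baseline LDL-C is thus a very strong predictor of the primary outcome.

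The cohorts come from different hospitals. PENELOPE required informed consent, whereas consent was waived for the control cohort (Protocol 12). A difference in baseline LDL-C or prior therapy is therefore plausible. Under section 10, whether the comparison is adjusted at all depends on a significance test and then on an undefined judgement about score distributions. A difference too small to be flagged can still move the primary result, and the shift would be read as an effect of the strategy.

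**Working it through.** The protocol states no share at target on admission, no expected attainment, no significance level and no power, so there is no figure of its own to reproduce. What follows is illustration.

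**Inputs from the protocol.** "Penelope patients ≤ 70 years old (N=663") in section 6a, and in section 6d: "A feasibility query in participating centres shows a cohort of 700-1200 candidates". So n = 663 against 700 to 1200.

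**Assumed.** b = share at or below 1.8 at baseline; r = share of these counted as reaching target; q = attainment in those above 1.8; two-sided 5% tests.

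**Formula.** Attainment in a cohort is p = b·r + (1 − b)·q.

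**Step 1. Shift when the strategy works.** Take q = 45% (CTRL) and 65% (PENELOPE), with r = 95%.
- b = 30% in both: CTRL 0.285 + 0.315 = 60.0%; PENELOPE 0.285 + 0.455 = 74.0%; difference 14.0 points.
- PENELOPE at b = 35%: 0.3325 + 0.4225 = 75.5%; difference 15.5; shift 1.5 points.
- CTRL at b = 25% instead: 0.2375 + 0.3375 = 57.5%; difference 74.0 − 57.5 = 16.5; shift 2.5 points.

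The shift is the difference in b times (r − q) for the cohort whose share moves: 0.05 × 0.30 to 0.05 × 0.50. A 10-point difference gives 3 to 5 points.

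**Step 2. Shift when the strategy does nothing.** Take q = 60% in both and r = 100%, with no adjustment. The paired values are for 700 and 1200 controls.

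| b, CTRL vs PENELOPE | p, CTRL vs PENELOPE | Spurious difference (OR) | False positives if unadjusted | Balance test flags it |
|---|---|---|---|---|
| 20% vs 25% | 68% vs 70% | 2 points (1.10) | 12.5% / 14.3% | 59.9% / 70.3% |
| 20% vs 30% | 68% vs 72% | 4 points (1.21) | 36.3% / 43.3% | 99.0% / 99.8% |

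First row with 700 controls:
- Outcome test: pooled p = 0.690, SE = √(0.690 × 0.310 × (1/700 + 1/663)) = 0.0251. The critical difference is 1.96 × 0.0251 = 0.049, and the chance that an expected 0.02 exceeds it in either direction is about 12.5%.
- Balance test: pooled b = 0.224, SE = √(0.224 × 0.776 × (1/700 + 1/663)) = 0.0226. The critical difference is 0.044, and (0.050 − 0.044)/0.0226 ≈ 0.25 gives 59.9% detection.

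The test therefore misses 20% vs 25% in 40% of cases with 700 controls and 30% with 1200.

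Two limits apply. The false-positive rates are for a comparison that is never adjusted, so they overstate the rate for the planned sequence where adjustment is triggered and works. And an unflagged sample must show a difference in share below about 4.4 points (700 controls), so the shift it carries is at most about 0.044 × 0.40 = 1.8 points in this scenario.

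**Step 3. Effect of including patients at target.** With equal b and r in both cohorts, the whole-population difference is (1 − b) times that in patients above 1.8. From 20 points: 0.85, 0.70 and 0.60 × 20 = 17, 14 and 12 points at b = 15%, 30% and 40%. With q = 60% vs 70%, r = 100% and 700 controls, power in all patients against those above 1.8 only is 90.9% vs 93.4% at b = 20%, 85.2% vs 90.0% at 30%, and 77.6% vs 85.1% at 40%. In these scenarios the smaller subgroup is not short of power.

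**The case against.** - **The protocol does plan adjustment.** A reader might infer that any baseline imbalance becomes an apparent strategy effect. The documents do not support that. Section 10 provides propensity adjustment in two forms, and lipid panels and baseline therapy are natural candidates for the score. A 10-point difference in the at-target share would almost always be flagged, if that status is among the variables tested. What remains is the moderate difference that the test lets through, and the fact that neither variable is named.
- **Dilution is not bias.** A reader might also infer that counting patients already at target distorts the effect. The stated objective concerns very high-risk patients as a whole (Protocol 4). For them, 14 points in the step 3 example is the correct answer; 20 points answers a different question. This objection stands in full. Secondary outcomes c and d also include a 50% reduction from baseline, which a patient already at 1.8 does not meet automatically.
- **The counting rule is partly inferred.** The protocol does not say that patients at target on admission are automatic successes. The outcome refers to the time after admission, so a later qualifying value appears to be needed. Whether the admission sample could itself qualify is not stated.
- **This may belong in the SAP.** Covariate lists commonly do, and their absence here is not the finding. But the protocol itself fixes the rule that correction takes place only in case of imbalance, and that rule is what needs replacing.

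**Conclusion.** The concern holds in a limited form. Because correction is conditional and does not name baseline LDL-C or baseline therapy, the primary comparison of two non-randomised cohorts can run unadjusted for what is likely its strongest predictor. Under the assumed rates, a 5-point difference in the share already at target shifts the result by about 1.5 to 2.5 points, and a balance test of 20% against 25% would miss it 30% to 40% of the time. That detection figure assumes at-target status is tested at all. The second condition, on score distributions, can only make adjustment less likely, whereas imbalance in other variables could trigger it. Bias is therefore possible, not automatic, and its actual size cannot be derived from the protocol. The whole-population outcome itself is not an error.

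**What to change.** In section 10, replace the conditional rule for these two variables: adjust the primary comparison for baseline LDL-C (continuous) and baseline lipid-lowering therapy in every case, whatever the balance tests show. Keep the whole-population result as primary. Pre-specify a supporting analysis in patients with baseline LDL-C above 1.8 mmol/L, those on whom the PENELOPE steps act at entry. One added sentence in section 8a should say whether the admission value itself can count as reaching target.

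The cost is wording, since the variables are already to be collected. There are two drawbacks. Control-cohort lipids come from routine records, so baseline LDL-C may be missing for some patients and will need the imputation that section 10 already foresees. The supporting analysis also uses fewer patients, although in the scenarios above it loses no power.
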